### **6.4. Medical/Surgical History Assessments**

Medical and surgical history will be obtained and evaluated at Screening to confirm the patient's eligibility to enroll in the study.

### **6.5. Electrocardiograms**

Twelve-lead electrocardiograms (ECGs) will be performed for all patients at Screening, at the end of the first infusion of study drug on Day 1, at EOT, and at the ET Visit. If clinically indicated, the 12-lead ECGs will be repeated as close as possible following the end of the infusion of study drug on the day on which the post-dose PK samples are drawn (Day 4 [ $\pm$ 1 day]; day selected at the discretion of the Investigator). All 12-lead ECGs will be performed after the end of the infusion and after the patient has been in a supine position for at least 10 minutes. The value at Screening will be used for assessing the QT interval corrected using Fridericia's formula (QTcF) exclusion criterion. All 12-lead ECGs will be performed and read locally. The following ECG parameters will be recorded:

- Heart rate,
- QRS interval,
- PR interval,
- RR interval,
- QT interval, and
- QTc interval.

All ECGs will be evaluated for the presence of abnormalities by a qualified local physician. The ECGs will be classified as 1 of the following:

- Normal,
- Having a not clinically significant abnormality, or
- Having a clinically significant abnormality.

An example of a clinically significant abnormality may be a corrected QTcF  $\geq$ 480 msec.

## **6.6. Physical Examinations**

A complete physical examination will be performed at Screening, Day 3, Day 5, Day 7, the EOT Visit, and the ET Visit. A limited physical examination will be performed, if needed, at Day 2, Day 4, Day 6, Day 8 to Day 14 (if EOT has not already occurred), the TOC Visit, and the LFU Visit.

A complete physical examination must include source documentation of weight, skin, head and neck, heart, lung, abdomen, extremities, back/flank/costo-vertebral angle tenderness, and neuromuscular assessments. Height will only be collected at Screening. Limited physical examinations are symptom-based. When clinically indicated, a prostate exam can be performed, at the discretion of the Investigator.

Physical examinations may be performed at unscheduled time points if deemed necessary by the Investigator.

## **6.7. Chest X-Ray/Radiology**

Chest X-rays, magnetic resonance imaging (MRI), or computed tomography (CT) scans will be performed in patients with HABP, VABP, or VP at Screening and the TOC Visit, and as clinically indicated to evaluate for the presence of infiltrates. Ultrasounds may also be performed for patients with HABP, VABP, or VP at Screening. If an ultrasound is performed, a confirmatory X-ray or CT scan should be performed within 24 hours. Imaging should be conducted per institutional guidelines and results recorded in the source documents and the eCRF.

## **6.8. Mechanical Ventilator Assessments**

Patients whose primary indication for enrollment into the study is HABP, VABP, or VP and who require mechanical ventilation support will be managed by the study Investigators per institutional guidelines. Data regarding mechanical ventilation settings will be captured in the source documents and the eCRFs.

## **6.9. Safety Monitoring and Assessment of Abnormal Liver Function Tests (LFT)**

Safety monitoring for LFTs will occur from randomization until 30 days following the last administration of study drug; however, any abnormal LFT will be monitored according to the Safety Monitoring Plan. Investigators should evaluate standard of care laboratory reports in addition to study laboratory reports when monitoring for LFTs.

## **6.10. Data Safety Monitoring Board (DSMB)**

An independent DSMB will review the safety data periodically. The DSMB will also review serious adverse events (SAE) and deaths on an ongoing basis. They will make recommendations to the Sponsor based on the safety data. The PK assessment report of data from the initial cohort of patients in Part A from the independent PK assessor will be submitted to the DSMB for its approval of continued enrollment and initiation of Part B. Further details regarding the DSMB guidelines will be described in the DSMB Charter.

# **7. PHARMACOKINETIC ASSESSMENTS**

Intense and sparse PK samples will be collected as outlined in Table 1. The PK samples obtained from the ETX2514SUL group will be analyzed for ETX2514 and sulbactam concentrations using a validated assay by an approved bioanalytical laboratory.

The actual PK sampling times will be captured on the eCRF. Actual dosing time will also be captured on the eCRF. Actual sampling time will be used for the PK calculations.

### **7.1. Intense Pharmacokinetic Sampling**

As described in Section 9.2.3 of the protocol, approximately 30 patients randomized in Part A had samples collected for intense PK analysis to ensure that exposures observed in this severely ill cohort are comparable to those observed thus far in prior clinical studies.

The intense PK sampling will also be performed on the first approximately 20 patients randomized in Part A from China Mainland sites.

### **7.2. Sparse Pharmacokinetic Sampling**

All other patients enrolled in the study (Parts A and B) will have samples collected for sparse PK analysis.

## **8. ANALYSIS POPULATIONS**

This study is designed to estimate treatment efficacy of ABC infections, with a pivotal component in Part A.

### **8.1. Intent-to-Treat Population (ITT)**

The ITT Population will include all patients randomized to study drug treatment (ETX2514SUL plus imipenem/cilastatin or colistin plus imipenem/cilastatin) in Part A or enrolled in Part B, regardless of whether the patient actually receives study drug.

### **8.2. Modified Intent-to-Treat Population (MITT)**

The MITT Population will include patients in Parts A and B who meet ITT criteria and receive any amount of study drug. The MITT Population will be considered the Safety Population. Patients with HABP/VABP/VP who were randomized to Part A on the basis of a BPP rapid test result, but were subsequently withdrawn due to a lack of a culture growing ABC, will be counted in the MITT and Safety Populations.

### **8.3. Microbiologically Modified Intent-to-Treat Population (m-MITT)**

The m-MITT Population will include patients who meet MITT criteria and have an ABC organism isolated as the qualifying culture specimen, as confirmed by the central and/or local microbiology laboratory. If an isolate for testing at the central laboratory is not available, the local laboratory data can be used to confirm the presence of ABC organism, as long as the local laboratory uses modern methods of diagnosis such as molecular based tests, MALDITOF, Vitek, Phoenix, etc (ie, not conventional biochemical or manual phenotypic methods). Patients with HABP/VABP/VP who are enrolled based upon a positive BPP rapid test for ABC, but subsequently are found to have respiratory sample cultures that do not grow ABC (by the local laboratory), will be withdrawn from the study drug treatment. These patients will not be

included in the m-MITT Population but will remain in the MITT Population.

#### **8.4. Carbapenem-resistant ABC m-MITT Population (CRABC m-MITT)**

For Part A, the CRABC m-MITT Population will include patients who meet m-MITT criteria and have a baseline ABC organism that is confirmed to be carbapenem-resistant (MIC to imipenem/meropenem  $\geq 8$  mg/L) by the central laboratory or by the local laboratory if the central laboratory is not able to identify the isolate for any reason. Patients will be excluded from the CRABC m-MITT Population if they have isolates that are deemed by the central laboratory to be resistant to ETX2514SUL (MIC  $>4$  mg/L) or colistin (MIC  $\geq 4$  mg/L), if their blood culture or respiratory samples are collected more than 72 hours prior to randomization, if they are transferred from Part A to Part B, or if they are enrolled with infections other than ABC pneumonia or bloodstream infection (ie, infections other than HABP, VABP, VP, and bacteremia). A sensitivity analysis for the primary efficacy endpoint will be performed for patients whose eligible culture is  $>48$  hours from the first dose of treatment, as well as for all patients with and without evidence of non-susceptibility to colistin and ETX2514SUL at baseline.

For Part B, the CRABC m-MITT Population will include patients who meet m-MITT criteria and have a baseline ABC organism that is confirmed to be carbapenem-resistant (MIC to imipenem/meropenem  $\geq 8$  mg/L) by the central laboratory or by the local laboratory if the central laboratory is not able to identify the isolate for any reason. Patients will be excluded from the CRABC m-MITT Population if their blood culture or respiratory samples are collected more than 72 hours prior to randomization.

#### **8.5. Clinical Evaluable Population (CE)**

The CE Population will include patients who meet m-MITT criteria and meet evaluability criteria (meet key inclusion criteria, do not have key exclusion criteria, received at least 72 hours of study drug [ie, 12 doses of ETX2514SUL plus 12 doses of imipenem/cilastatin or 6 doses of colistin plus 12 doses of imipenem/cilastatin in patients without dose adjustments] to be a clinical cure, received at least 48 hours of study drug [ie, 8 doses of ETX2514SUL plus 8 doses of imipenem/cilastatin or 4 doses of colistin plus 8 doses of imipenem/cilastatin in patients without dose adjustments] to be a clinical failure, received  $\geq 80\%$  of anticipated doses, and did not have a clinical response of indeterminate at the TOC Visit).

#### **8.6. Microbiologic Evaluable Population (ME)**

The ME Population will include patients who meet m-MITT criteria and CE criteria and have an appropriately collected culture specimen and interpretable culture result when specimen collection is clinically indicated at the TOC Visit.

#### **8.7. Carbapenem-resistant ABC Microbiologic Evaluable Population (CRABC ME)**

The CRABC ME Population will include patients who meet both ME criteria and CRABC m-MITT criteria.

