The CRABC m-MITT Population will include patients who meet m-MITT criteria and have a baseline ABC organism that is confirmed to be carbapenem-resistant (MIC to imipenem/meropenem  $\geq 8$  mg/L) by the central laboratory or by the local laboratory if the central laboratory is not able to identify the isolate for any reason. Patients will be excluded from the CRABC m-MITT Population if they have isolates that are deemed by the central laboratory to be resistant to ETX2514SUL (MIC  $> 4$  mg/L) or colistin (MIC  $\geq 4$  mg/L), if their blood culture or respiratory samples are collected more than 72 hours prior to randomization, if they are transferred from Part A to Part B, or if they are enrolled with infections other than ABC pneumonia or bloodstream infection (ie, ABC infections other than HABP, VABP, VP, and bacteremia). A sensitivity analysis for the primary efficacy endpoint will be performed for patients whose eligible culture is  $> 48$  hours from the first dose of study drug, as well as for all patients with and without evidence of non-susceptibility to colistin and ETX2514SUL at baseline.

The CE Population will include patients who meet m-MITT criteria and meet evaluability criteria (meet key inclusion criteria, do not have key exclusion criteria, received at least 72 hours of study drug [ie, 12 doses of ETX2514SUL plus 12 doses of imipenem/cilastatin or 6 doses of colistin plus 12 doses of imipenem/cilastatin in patients without dose adjustments] to be a clinical cure, received at least 48 hours of study drug [ie, 8 doses of ETX2514SUL plus 8 doses of imipenem/cilastatin or 4 doses of colistin plus 8 doses of imipenem/cilastatin in patients without dose adjustments] to be a clinical failure, received  $\geq 80\%$  of anticipated doses, and did not have a clinical response of indeterminate at the TOC Visit).

The ME Population will include patients who meet m-MITT criteria and CE criteria and have an appropriately collected culture specimen and interpretable culture result when specimen collection is clinically indicated at the TOC Visit.

The CRABC ME Population will include patients who meet ME criteria and who have a baseline ABC organism that is confirmed to be carbapenem-resistant (and susceptible to ETX2514SUL for Parts A and B and susceptible to colistin for Part A).

The PK Population will include patients who receive any amount of study drug and have evaluable PK data.

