#### **Sensitivity Analyses**

Sensitivity analyses of the primary efficacy endpoint will be conducted as follows:

- Analysis of the primary efficacy endpoint will be performed for patients whose eligible culture is >48 hours prior to the first dose of treatment in the CRABC m-MITT Population.
- Analysis of the primary efficacy endpoint will be performed for patients whose eligible culture is ≤48 hours prior to the first dose of treatment in the CRABC m-MITT Population.
- Analysis of the primary efficacy endpoint will be performed for patients with ABC pathogens susceptible to ETX2514SUL and colistin at baseline in the CRABC m-MITT Population.
- Analysis of the primary efficacy endpoint will be performed for patients without ABC susceptibility results for ETX2514SUL or colistin at baseline in the CRABC m-MITT Population.
- Analysis of the primary efficacy endpoint will be performed including the patients who were randomized into Part A but then transferred into Part B in the ITT Population.
- Analysis of the primary efficacy endpoint will be performed excluding the patients who have missing survival status in the CRABC m-MITT Population.

Analysis of the primary efficacy endpoint and the sensitivity analysis will be repeated including the patients who withdraw consent from the survival status.

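### SAP 8.7 omits the protocol's ETX2514SUL susceptibility condition for CRABC ME in Part B and weakens the susceptibility rule in Part A

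*SAP*

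**What the plan says.** Protocol 9.1 (Analysis Populations) builds CRABC ME from the ME criteria plus a positive condition on the baseline organism. It must be "confirmed to be carbapenem-resistant (and susceptible to ETX2514SUL for Parts A and B and susceptible to colistin for Part A". The synopsis repeats this.

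SAP 8.7 replaces that wording with a cross-reference: "The CRABC ME Population will include patients who meet both ME criteria and CRABC m-MITT criteria". It has no susceptibility wording of its own, so everything depends on what SAP 8.4 supplies, and SAP 8.4 defines CRABC m-MITT separately by part.

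- **Part A:** "Patients will be excluded from the CRABC m-MITT Population if they have isolates that are deemed by the central laboratory to be resistant to ETX2514SUL". The limit given there is an MIC above 4 mg/L, with a matching exclusion for colistin (MIC of 4 mg/L or more). Carbapenem resistance itself may be confirmed "by the local laboratory if the central laboratory is not able to identify the isolate for any reason".
- **Part B:** the only exclusion given is sample age: "Patients will be excluded from the CRABC m-MITT Population if their blood culture or respiratory samples are collected more than 72 hours prior to randomization".

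The other component, ME (SAP 8.6), requires m-MITT and CE status and that patients "have an appropriately collected culture specimen and interpretable culture result when specimen collection is clinically indicated at the TOC Visit".

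SAP 9.3.1 plans a sensitivity analysis of "patients without ABC susceptibility results for ETX2514SUL or colistin at baseline in the CRABC m-MITT Population", so the SAP expects such patients in the parent population.

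**The concern.** The two documents give one name to two different sets of patients. CRABC ME carries named secondary endpoints in SAP 5.2 and 9.3.2: clinical cure at EOT, TOC and LFU, microbiological response at the same visits, and 28-day mortality. In Part A these come with 95% confidence intervals for the treatment difference. A reader who takes the definition from the protocol will assume that every patient behind those rates had an organism shown to be susceptible to ETX2514SUL and, in Part A, to colistin. Under the SAP that need not be so. Microbiological response is where this matters most.

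The SAP neither flags nor justifies the change. SAP 1 promises only that departures from the SAP after database lock will be documented in the study report. An analysis that follows SAP 8.7 exactly would not count as a departure, so the report need not mention the difference from the protocol.

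**Working it through.** The plan gives no figure to reproduce here. The check compares two inclusion rules.

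**Inputs**
- Protocol rule (9.1): ETX2514SUL-susceptible in Parts A and B, and colistin-susceptible in Part A.
- SAP rule (8.7 through 8.4): in Part A, not found resistant to either drug by the central laboratory; in Part B, no susceptibility condition.
- Categories (SAP 9.2.4): ETX2514SUL susceptible at MIC of 4 mg/L or less, otherwise resistant; colistin susceptible below 4 mg/L, otherwise resistant. With only two categories, not resistant and susceptible differ only where no result exists.

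**Does another SAP section restore the condition?** SAP 8.6 (ME) has no susceptibility criterion. SAP 8.5 (CE) refers to key exclusion criteria without listing them. If Protocol Exclusion 27 is among them, it covers only colistin in Part A, and only resistance known at entry. No exclusion criterion concerns ETX2514SUL. SAP 9.1.1 allows local data where central data are missing, but that names a data source and does not create an entry condition.

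**Rule comparison.** Take patients who meet ME, are carbapenem-resistant and satisfy the 72-hour rule. Each drug result is S (susceptible), R (resistant; central result in Part A) or none. That gives 2 parts × 3 × 3 = 18 combinations.

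| Part | Admitted by protocol | Admitted by SAP | Admitted by SAP only |
|---|---|---|---|
| A | 1 (S to both drugs) | 4 (neither drug R) | 4 − 1 = 3 |
| B | 3 (ETX2514SUL S, any colistin result) | 9 (all) | 9 − 3 = 6 |
| Total | 4 | 13 | 9 of 18 |

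- The three Part A differences all involve a missing result: ETX2514SUL S with no colistin result, no ETX2514SUL result with colistin S, and neither result.
- The six Part B differences are ETX2514SUL R (three colistin states) and no ETX2514SUL result (three colistin states).
- In all nine the SAP admits a patient whom the protocol excludes.
- Six of the nine rest on reading the protocol's wording as requiring a result, which is its natural sense. The three with an ETX2514SUL-resistant isolate in Part B do not depend on that reading.

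**A further Part A case.** The SAP 8.4 exclusion names the central laboratory. A patient whose colistin resistance is known only from the local laboratory is therefore not caught by its wording. Protocol 3.1 lets such a patient stay in Part A if Part B is not yet open in the country and the patient is responding. Protocol 7.7 says instead that study drug is withdrawn when Part B is not open, so how often this arises depends on how those two sections are reconciled.

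**Size per added patient.** Adding one patient with outcome y (0 or 1) to n patients with rate p changes the rate by (y − p)/(n + 1). The rate p = 0.40 and the group sizes are assumptions.
- n = 40: (1 − 0.40)/41 = +1.5 points; (0 − 0.40)/41 = −1.0 points.
- n = 20: (1 − 0.40)/21 = +2.9 points; (0 − 0.40)/21 = −1.9 points.

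**The case against.** The strongest reply is that little of consequence depends on this, and several parts of it stand.

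- In Part A, the only comparative part, isolates found resistant by the central laboratory are excluded under both documents. A reader might infer that the SAP abandons the susceptibility rule altogether. In Part A it is loosened; only in Part B is it absent.
- A reader might treat CRABC ME as the per-protocol set for non-inferiority and conclude that the main claim is at risk. The documents do not support this. Non-inferiority is assessed in Part A CRABC m-MITT (SAP 9.3.1), CRABC ME has no margin or decision rule, and Part B is non-randomized and descriptive.
- Other planned outputs show the affected patients. SAP 9.3.1 analyses mortality separately with and without susceptibility results, SAP 9.3.3 tabulates cure and microbiological response by ETX2514SUL MIC in CRABC m-MITT for both parts, SAP 9.2.4 summarizes MICs in CRABC ME, and SAP 9.2.1 lists each patient's population status.
- The SAP is narrower than the protocol in one respect. Through CRABC m-MITT it brings in the 72-hour exclusion and, in Part A, the transfer exclusion, neither of which appears in the protocol's CRABC ME sentence.
- The SAP cites protocol version 4.0, and the version of the supplied protocol cannot be seen, so a change between versions cannot be ruled out.

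These points limit the consequence. They do not remove the conflict: none of the listed outputs corrects the CRABC ME rates, and nothing in the SAP records the broader set as a choice.

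**Conclusion.** The conflict is real, and it is an error as written, not a missing detail. Following SAP 8.7 puts patients whom the protocol excludes into named secondary analyses. In Part B these include patients with ETX2514SUL-resistant isolates.

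The reach is limited to the CRABC ME results. The primary analysis and the sample size are untouched.

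The total size is unknown, because neither document counts resistant or untested isolates. The per-patient figures illustrate scale only and rest on the assumed 40% rate and the assumed group sizes. Two larger readings should be avoided:
- Dividing 1 by n (2.5 points at 40, 5 points at 20) gives the effect of reversing one patient's outcome, not of adding a patient.
- Multiplying an assumed missing-result rate by 120 gives at most a ceiling for Part A. For example, 0.05 × 120 = 6, but 120 is the CRABC m-MITT target, and those patients must still meet the CE and ME criteria to enter CRABC ME.

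**What to change.** Amend SAP 8.7 to add the protocol's condition: a baseline ABC isolate with ETX2514SUL MIC of 4 mg/L or less (Parts A and B) and colistin MIC below 4 mg/L (Part A). Use the central result or, where there is none, the local result, in line with SAP 9.1.1. State that patients with no result are not in CRABC ME.

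This does not simply return to the protocol, because the cross-reference to CRABC m-MITT still brings in the 72-hour and transfer exclusions. The SAP should say whether those are intended.

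If the broader set was deliberate, record the reason in the SAP and report the protocol-defined set alongside it.

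The cost is a sentence or two of SAP text and a few patients fewer in CRABC ME. It needs no new data.

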## **8.8. Pharmacokinetic (PK) Population**

The PK Population will include patients who receive any amount of study drug and have evaluable PK data.

## **9. STATISTICAL ANALYSIS**

### **9.1. General Statistical Considerations**

#### **9.1.1. General Analysis Approach**

Continuous variables will be summarized using the number of non-missing observations, arithmetic mean, standard deviation, median, minimum, and maximum values as descriptive statistics. Categorical variables will be summarized by using the frequency count and the percentage of patients in each category as descriptive statistics.

All comparisons in Part A will be for ETX2514SUL plus imipenem/cilastatin versus colistin plus imipenem/cilastatin. The efficacy endpoints for Part B will be summarized separately and will be used to supplement results in Part A. Listings of individual patient data will be produced.

Data from central microbiology laboratory will be used for microbiological analysis. If the data from central microbiology laboratory is not available, the data from local microbiology laboratory will be used.

